10.1.2 Reporting Unanticipated Problems

Unanticipated problem reporting will begin at the time of participant consent. The Unanticipated Problem Form will be submitted to the CRS Compliance Office within 1 business day of becoming aware of the Unanticipated Problem.

When becoming aware of new information about an Unanticipated Problem, submit the updated information to CRS Compliance with an updated Unanticipated Problem Form. The site Investigator or designated research personnel will report all unanticipated problems, whether related or unrelated to the investigational agent(s) to the **IRB in accordance with their local institutional guidelines.**

11.0 DATA SAFETY AND MONITORING

The Principal Investigator, Sub-Investigator, and Clinical Research Coordinators shall meet on a monthly basis to review toxicities and follow up on results of patients enrolled on the study.

The adequacy of the data and safety monitoring plan will be reviewed by the Inova Schar Cancer Institute's Protocol Review and Monitoring Committee (PRMC). The PRMC shall also determine the risk level of the proposed trial, which in turn determines the frequency of review by the Data and Safety Monitoring Committee (DSMC).

All Severe Adverse Events (SAEs) are required to be reported to the appropriate Institutional Review Board (IRB). Based on SAEs, the IRB retains the authority to close the study to further accrual pending more detailed reporting and/or modifications to further reduce risk and maximize the safety of participating patients.

Progress on the trial and the toxicities experienced will be reviewed by the DSMC. The DSMC shall review trial progress, protocol adherence, data management, and patient safety parameters, including rates of adverse events and serious adverse events, on a schedule determined by the trial's risk level. They shall also include reviews performed by selected reviewers and auditors. Results from these DSMC reviews and the Committee's recommendations shall be forward to the Principal Investigator, the Research Oversight Committee, and the appropriate Institutional Review Board.

If the DSMC recommends a study change for patient safety or efficacy reasons, or that accrual be halted, the PI will be notified immediately, as will the PRMC and IRB.

In the unlikely event that the trial PI does not concur with the DSMC, the ISCI CEO/Director must be informed of the reason for the disagreement. The trial PI, DSMC Chair, and ISCI Director will be responsible for reaching a mutually acceptable decision about the study. Confidentiality must be preserved during these discussions. However, in some cases, relevant data may be shared with other selected trial investigators and staff to seek advice to assist in reaching a mutually acceptable decision.

12.0 STATISTICAL CONSIDERATIONS

It is highly likely that the antitumor activity of ketoconazole and abiraterone in prostate cancer depend substantially on the ability of both agents to inhibit CYP 17A1 and disrupt androgen synthesis. We and others have shown that antitumor effects of abiraterone are substantially reduced in patients in whom ketoconazole has previously failed to be effective. In addition, enzalutamide, whose mechanism is not CYP17A1 dependent, does inhibit CRPC through disruption of androgen signaling. There are essentially no data regarding the success of ketoconazole therapy after abiraterone "failure". If ketoconazole and abiraterone share the same mechanism of action one would expect the same low PSA response rate in men with CRPC who receive (I) ketoconazole → abiraterone and those who receive (II) abiraterone → ketoconazole. If the response rate among men treated with sequence (II) substantially exceeds the PSA RR of 10% we saw with sequence (I), this would suggest additional effects of ketoconazole. Further, the hypothesis of RPCI I68905 is that ketoconazole also inhibits CYP24A1, the predominant vitamin D metabolizing enzyme and hence potentiates the antitumor effect of calcitriol (1,25 dihydroxycholecalciferol, 1,25 vitamin D₃) - in a synergistic manner.

This study proposes to treat men in whom abiraterone has proven to be ineffective within 12 months of entry onto this portion of this study. Based on the above, a PSA response rate of 10% or less for this regimen following abiraterone failure would be considered to have too little activity to be of clinical significance in this patient population, whereas a response rate of 40% or more would be of interest. We utilize a flexible design (Chen TT, NG T. Optimal flexible designs in phase II clinical trials. *Stat Med.* 1998;17:2301-2312.) that permits the actual number of evaluable patients in each stage to vary slightly in order to accommodate the challenges of accruing precise numbers of evaluable patients. In the first stage, we target an accrual of 9 eligible and evaluable patients but permit accrual to range from 7 to 11 patients. If more than 0 patients respond and medical judgment indicates, accrual to the second stage of the trial will be initiated; otherwise, the study will be stopped and the treatment regimen will be classified as clinically uninteresting. If the study advances to the second stage, then an overall study accrual of 15 eligible and evaluable patients will be targeted but will be permitted to range from 13 to 17 patients. If more than 2 out of 13-14 patients respond or 3 out of 15-17 patients respond then the regimen will be considered worthy for additional investigation. If the true response rate is 10% (H_0), these decision rules limit the average probability of designating the treatment as active to 10% and the average probability of stopping after completing only the first stage of accrual is 39%. On the other hand, if the true response rate is 40% (H_1) then the average probability of correctly classifying the treatment as active is 93%. These are average probabilities computed from the individual probabilities averaged over all permitted accrual combinations and assuming each combination is equally likely. Limited investigations have indicated that the type I and type II errors are fairly insensitive to variations in the true probability distribution of accrual combinations.

Stage of Accrual	Targeted Cumulative Accrual	Limits of Actual Accrual	Max number of responses to reject H_1
1	9	7-11	0/(7-11)
2	15	13-17	2/(13-14), 3/(15-17)

Entry criteria for this addendum phase will be identical to the ongoing trial except that progressive disease will be required to have occurred on abiraterone within the prior 12 months. Patient may also not have received enzalutamide in order to, as much as possible, “standardize” prior manipulation of the androgen axis.

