12.2 Analysis of Secondary Endpoints

Toxicity will be graded according to the NCI CTC version 4.03 and relationship to study drug will be assessed. Toxicities will be tabulated by dose of calcitriol. All patients who receive study drug will be considered evaluable for toxicity.

Objective tumor response will be judged by monthly physical exam and radiographic evaluation which will be done q12 weeks. Patients will be considered evaluable for tumor response if they have at least two post-baseline tumor assessments at least 4 weeks apart, received study medication for 8 weeks or if they have evidence of disease progression.

Analysis of the correlative studies in section 8.0 will be descriptive.

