5 REPORTING OF RESULTS

All patients included in the study must be assessed for response to treatment, even if there are major protocol treatment deviations or if they are ineligible. Each patient will be assigned one of the following categories: 1) complete response, 2) partial response, 3) stable disease, 4) progressive disease, 5) early death from malignant disease, 6) early death from toxicity, 7) early death because of other cause, or 9) unknown (not assessable, insufficient data). (*Note:* By arbitrary convention, category 9 usually designates the "unknown" status of any type of data in a clinical database.)

All of the patients who met the eligibility criteria should be included in the main analysis of the response rate. Patients in response categories 4-9 should be considered as failing to respond to treatment (disease progression). Thus, an incorrect treatment schedule or drug administration does not result in exclusion from the analysis of the response rate. Precise definitions for categories 4-9 will be protocol specific.

All conclusions should be based on all eligible patients.

Subanalyses may then be performed on the basis of a subset of patients, excluding those for whom major protocol deviations have been identified (e.g., early death due to other reasons, early discontinuation of treatment, major protocol violations, etc). However, these subanalyses may not serve as the basis for drawing conclusions concerning treatment efficacy, and the reasons for excluding patients from the analysis should be clearly reported. The 95% confidence intervals should be provided.

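### The PSA go/no-go rule counts evaluable men without defining PSA-evaluable, while Appendix B bases conclusions on all eligible men; with 3 responders, one exclusion reverses the result

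*Combined protocol and SAP*

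**What the plan says.** Section 12.0, repeated in the synopsis, counts the same kind of patient at both stages: "In the first stage, we target an accrual of 9 eligible and evaluable patients" and later "an overall study accrual of 15 eligible and evaluable patients will be targeted". Stage 1 may hold 7 to 11 men, and the trial stops if none responds. The final count may be 13 to 17. The largest number of responses that still fails is 2 for 13–14 men and 3 for 15–17 men.

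Three places bear on who is evaluable, and none settles it for PSA:

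- **Section 12.2**, under secondary endpoints: "Patients will be considered evaluable for tumor response if they have at least two post-baseline tumor assessments at least 4 weeks apart". Eight weeks of study drug or evidence of progression also qualifies. The section ties tumor response to physical examination and radiographs.
- **Section 8.2** requires two PSA values at least 4 weeks apart. It does not say whether a man without them is excluded or is a non-responder.
- **Inclusion criterion 3** calls an elevated PSA evaluable disease. That describes disease at entry, not the analysis set.

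Appendix B section 5 gives a different denominator: "All of the patients who met the eligibility criteria should be included in the main analysis of the response rate". Its categories include "9) unknown (not assessable, insufficient data", and "Patients in response categories 4-9 should be considered as failing to respond to treatment (disease progression". It then says "All conclusions should be based on all eligible patients". On subsets that leave out, for example, men who stopped treatment early, it says "these subanalyses may not serve as the basis for drawing conclusions concerning treatment efficacy".

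**The concern.** The primary decision rests on a denominator that one part of the plan leaves undefined and another part contradicts. Excluding a man without a response can only raise the observed rate, so the open choice works in one direction. The final cutoff also steps up between 14 and 15 patients. That step belongs to the disclosed flexible design and is not itself a fault. The fault is that an undefined evaluability rule lets the count cross the step once responses are visible.

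Borderline men are foreseeable. The calendar in section 7.0 draws PSA at weeks 5 and 9, so a man who leaves before week 9 lacks two scheduled on-treatment values. Section 5.2 takes men off study for most drug-related grade 3–4 non-hematopoietic toxicity. The trial is open and single-arm, and under section 11.0 the investigators meet monthly over toxicities and results.

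**Working it through.** **Inputs (section 12.0).** Null rate 10%; target rate 40%; stage 1 size n1 = 7–11 (target 9); total N = 13–17 (target 15); continue if at least one man responds; failure limit c = 2 for N = 13–14 and c = 3 for N = 15–17; averages taken with equal weight over the 25 permitted pairs.

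**Formula.** With X1 ~ Bin(n1, p) and X2 ~ Bin(N − n1, p):

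P(active) = Σ over x1 ≥ 1 of P(X1 = x1) × P(X2 ≥ c + 1 − x1).

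**Step 1: reproduce the plan.**

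| | Computed | Stated |
|---|---|---|
| Average type I error | 9.73% | 10% |
| Average early stop at 10% | 39.17% | 39% |
| Average power at 40% | 93.50% | 93% |

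The sentence on 15–17 patients could be read as saying that 3 responders suffice. That reading gives type I error 17.6% and power 96.2%, which does not match, so the table's limits are the operative rule.

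**Step 2: the step in the cutoff.** With n1 = 9 and p = 0.10, P(active) by final N is 13.2% (13), 15.5% (14), 5.5% (15), 6.7% (16) and 8.1% (17). Three of 15 does not exceed 3, so it is not active. Three of 14 exceeds 2, so it is active.

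**Step 3: how often one exclusion decides.** For n1 = 9 and p = 0.10:

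- Exactly 3 of 15: 455 × 0.1³ × 0.9¹² = 0.1285.
- Less the paths stopped at stage 1: 0.9⁹ × [20 × 0.1³ × 0.9³] = 0.3874 × 0.01458 = 0.0056.
- Result: 0.1285 − 0.0056 = 0.1229 (0.113 at n1 = 7; 0.127 at n1 = 11).

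At n1 = 9 and true rates of 20%, 30% and 40% the probability is 23.9%, 16.3% and 6.1%.

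**Step 4: worst case.** If one non-responder is excluded every time step 3 occurs, type I error at 9/15 is 0.0551 + 0.1229 ≈ 0.178.

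**Step 5: one man who cannot respond.** Assume 15 eligible men, one of them without usable PSA values, and nine evaluable men in stage 1. Excluding him and using the 14-man limit gives P(active) 15.5% at a rate of 10% and 95.7% at 40%. Keeping him as a non-responder under the 15-man limit gives 4.4% and 87.5%.

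**Step 6: routine exclusion (illustration).** Assume that a share d of eligible men is excluded, that all of them are non-responders, and that the 10% null is an all-eligible rate. The rate among evaluable men is then 0.10/(1 − d).

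| d | Rate among evaluable men | Average type I error | Type I error at 9/15 |
|---|---|---|---|
| 0 | 0.100 | 9.7% | 5.5% |
| 5% | 0.105 | 11.1% | 6.4% |
| 10% | 0.111 | 12.7% | 7.6% |
| 20% | 0.125 | 16.8% | 10.7% |

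The documents give no exclusion rate, so the values of d are assumptions. Section 12.0 does not give the denominator behind its 10%. If that was an evaluable-only rate, the stated error holds.

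**The case against.** **The 12.2 rule may already cover PSA.** Section 8.1 names the NCI PSA criteria alongside RECIST for objective tumor response, so 12.2 could be read as reaching PSA. Men with documented progression would then stay in the denominator. This narrows the gap but does not close it. The 12.2 rule sits under secondary endpoints and names only examination and radiographs. It could still exclude a man who stopped early without progression, which Appendix B section 5 does not allow as a basis for conclusions.

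**Appendix B is largely general guidance.** That is true of much of it, and its section 5 leaves precise category definitions to the protocol. But section 8.1 refers to it, its section 2.2.6 carries this trial's PSA criteria, and its section 3.2.3 asks each protocol to define nonevaluability. Setting Appendix B aside would leave the primary denominator undefined. Treating it as binding would leave section 12.0 in conflict with it.

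**The effect is narrow.** This stands. The reversal at 3 responders needs 15–17 eligible and 13–14 evaluable men. During accrual an unevaluable man might be replaced. The stage 1 limit of 0 is the same for every permitted stage 1 size.

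**Defining PSA-evaluable in advance would be enough.** It would remove the after-the-fact choice without reducing power. It would not reconcile section 12.0 with Appendix B section 5.

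**Conclusion.** The concern holds and should be fixed before analysis. Two stated rules conflict on the denominator of the primary decision, and the one in section 12.0 uses an undefined term. The plan's arithmetic is sound on its own terms.

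The exposure is specific: with exactly 3 responders among 15, one exclusion turns the result from not active to active. At a true rate of 10% and nine men in stage 1, that situation has probability 12.3%. The 17.8% type I error is an upper bound that requires an exclusion every time; nothing in the documents suggests that this is intended. The step 6 averages of 11.1% to 16.8% illustrate sensitivity under the assumptions given there.

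**What to change.** In section 12.0 and the synopsis, before analysis:

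1. Make all eligible patients the primary denominator, in line with Appendix B section 5.
2. Count any man without a confirmed PSA response as a non-responder, including men with missing PSA or early withdrawal.
3. Apply the stage 1 (7–11) and final (13–17) cutoffs to responders among all eligible patients.
4. Define a PSA-evaluable set in advance and report its response rate with a 95% confidence interval as a sensitivity analysis only.
5. State in section 12.2 that its evaluability rule applies to tumor response only.

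The cost is text in three places and no new data collection. The reported rate may be lower. If the 40% target was meant for evaluable men, and a share d of eligible men cannot be evaluated, the all-eligible rate is 0.40 × (1 − d):

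| d | All-eligible rate | Average power | Power at 9/15 |
|---|---|---|---|
| 0 | 0.40 | 93.5% | 90.8% |
| 5% | 0.38 | 91.4% | 87.9% |
| 10% | 0.36 | 88.7% | 84.5% |
| 20% | 0.32 | 81.6% | 75.5% |

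The team should therefore confirm which population the 10% and 40% rates describe.

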This study proposes to treat men in whom abiraterone has proven to be ineffective within 12 months of entry onto this portion of this study. Based on the above, a PSA response rate of 10% or less for this regimen following abiraterone failure would be considered to have too little activity to be of clinical significance in this patient population, whereas a response rate of 40% or more would be of interest. We utilize a flexible design (Chen TT, NG T. Optimal flexible designs in phase II clinical trials. *Stat Med*. 1998;17:2301-2312.) that permits the actual number of evaluable patients in each stage to vary slightly in order to accommodate the challenges of accruing precise numbers of evaluable patients. In the first stage, we target an accrual of 9 eligible and evaluable patients but permit accrual to range from 7 to 11 patients. If more than 0 patients respond and medical judgment indicates, accrual to the second stage of the trial will be initiated; otherwise, the study will be stopped and the treatment regimen will be classified as clinically uninteresting. If the study advances to the second stage, then an overall study accrual of 15 eligible and evaluable patients will be targeted but will be permitted to range from 13 to 17 patients. If more than 2 out of 13-14 patients respond or 3 out of 15-17 patients respond then the regimen will be considered worthy for additional investigation. If the true response rate is 10% (H_0), these decision rules limit the average probability of designating the treatment as active to 10% and the average probability of stopping after completing only the first stage of accrual is 39%. On the other hand, if the true response rate is 40% (H_1) then the average probability of correctly classifying the treatment as active is 93%. These are average probabilities computed from the individual probabilities averaged over all permitted accrual combinations and assuming each combination is equally likely. Limited investigations have indicated that the type I and type II errors are fairly insensitive to variations in the true probability distribution of accrual combinations.

Stage of Accrual	Targeted Cumulative Accrual	Limits of Actual Accrual	Max number of responses to reject H_1
1	9	7-11	0/(7-11)
2	15	13-17	2/(13-14), 3/(15-17)

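### The stated 10% type I error averages rates from 5.3% to 15.8% over the permitted sample sizes, and nothing requires the final N to be set independently of the responses

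*Combined protocol and SAP*

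**What the plan says.** Section 12.0, repeated in the synopsis under Statistical Analysis, describes a two-stage flexible design.

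- **Hypotheses.** "a PSA response rate of 10% or less for this regimen following abiraterone failure would be considered to have too little activity", whereas "a response rate of 40% or more would be of interest".
- **Stage 1.** The target is 9 evaluable patients (7 to 11 allowed). The trial stops if none responds.
- **Final N.** "an overall study accrual of 15 eligible and evaluable patients will be targeted but will be permitted to range from 13 to 17 patients".
- **Success bar.** More than 2 responders at N = 13 or 14, and more than 3 at N = 15 to 17. The sentence on the second bar could be read as 3, but the table gives 3 as the largest count that still fails.
- **Operating characteristics.** "these decision rules limit the average probability of designating the treatment as active to 10" percent; "the average probability of stopping after completing only the first stage of accrual is 39" percent; under 40%, "then the average probability of correctly classifying the treatment as active is 93" percent. These are "averaged over all permitted accrual combinations and assuming each combination is equally likely".
- **Robustness.** The paragraph closes by saying that both error rates change little if the accrual combinations are distributed differently. It gives no figures.

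The stated reason for the range is the difficulty of accruing an exact number of evaluable patients. Section 11.0 says that the investigators and coordinators "shall meet on a monthly basis to review toxicities and follow up on results of patients enrolled on the study". The synopsis describes a single-arm trial at one center. No section says who fixes the final N, when, or that this must be done without regard to PSA responses.

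**The concern.** Averaging over N with fixed weights treats N as if it were drawn without reference to the outcomes. Here the people who run accrual also see the outcomes, and the bar steps up by one responder between 14 and 15 patients. With exactly 3 responders among 14, closing accrual makes the regimen worthy of further study. Enrolling a fifteenth patient who does not respond makes it a failure. Both courses comply with the written rule.

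This is the trial's only formal efficacy decision. A later reader could not tell whether N = 14 came from logistics or from the count in hand. Even if it came from logistics, the error rate that applied would be well above the 10% quoted.

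**Working it through.** **Inputs** (section 12.0): p0 = 0.10; p1 = 0.40; stage-1 size n1 = 7 to 11; N = 13 to 17; bar c = 3 for N = 13 or 14 and c = 4 for N = 15 to 17. For the delay check: a PSA response needs two values at least 4 weeks apart (section 8.2), PSA is drawn every 4 weeks starting in week 5 (section 7.0), and accrual is 2 to 3 patients a month (synopsis).

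**Formula.** P(active) = P(Bin(N, p) ≥ c) − (1 − p)^n1 × P(Bin(N − n1, p) ≥ c). The second term removes trials with no responder in stage 1.

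**Step 1: reproduce the plan.** Equal weight on the 25 pairs (n1, N) gives:

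- type I error 9.73% (stated 10%)
- stopping after stage 1 under p0, the mean of 0.9^n1, 39.17% (stated 39%)
- power 93.50% (stated 93%)

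Reading the second bar as 3 instead of 4 would give an average type I error of 17.6%, so the table's reading is the intended one.

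**Step 2: split the average by N** (p = 0.10).

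| N | bar | type I error, n1 = 9 | range, n1 = 7 to 11 | mean over n1 |
|---|---|---|---|---|
| 13 | 3 | 13.2% | 12.6–13.4% | 13.13% |
| 14 | 3 | 15.5% | 14.6–15.8% | 15.36% |
| 15 | 4 | 5.5% | 5.3–5.6% | 5.47% |
| 16 | 4 | 6.7% | 6.4–6.8% | 6.68% |
| 17 | 4 | 8.1% | 7.6–8.2% | 8.00% |

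The last column averages to (13.13 + 15.36 + 5.47 + 6.68 + 8.00)/5 = 9.73%.

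Two entries written out for n1 = 9, where 0.9^9 = 0.38742:

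- N = 14: 0.15836 − 0.38742 × 0.00856 = 0.1550
- N = 15: 0.05556 − 0.38742 × 0.00127 = 0.0551

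**Step 3: let N follow the responses.** Close at 14 with 3 or more responders; otherwise go to 17 and require 4. Checking after every patient from 13 on gives the same result, because 3 responders by patient 13 are still there at patient 14, and 4 by patient 15 or 16 are still there at 17. For n1 = 9, the part added to a fixed N = 14 is:

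- 2 responders at 14 with at least one in stage 1: 0.25701 − 0.38742 × 0.0729 = 0.22877. At least 2 of the next 3 respond: 0.028. Product 0.0064.
- 1 responder at 14, in stage 1: 9 × 0.1 × 0.9^13 = 0.22877. All of the next 3 respond: 0.001. Product 0.0002.

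Total: 0.1550 + 0.0064 + 0.0002 ≈ 0.162. For n1 = 7, 8, 9, 10 and 11 the results are 15.2%, 15.8%, 16.2%, 16.4% and 16.5%.

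**Step 4: allow for delay.** Assume that accrual does not pause and that the team closes at 14 only if 3 responders are already known, otherwise going to 17. Mean type I error over n1:

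| patients pending at 14 | 1 | 2 | 3 | 4 | 5 | 6 |
|---|---|---|---|---|---|---|
| type I error | 14.4% | 13.0% | 11.8% | 10.7% | 9.9% | 9.3% |

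On the study calendar a confirmed response is known at about week 9. At 2 to 3 patients a month, two months' delay means 4 to 6 pending.

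**The case against.** **The plan limits an average, and the average is right.** This stands. Section 12.0 never claims 10% at each N. A reader might infer that the stated error rate is miscalculated or that a limit is broken; the documents do not support that.

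**Most of the excess is not optional stopping.** This also stands. A reader might infer that a data-driven N carries type I error from 10% to 16.5%. But N = 14 fixed in advance, with no look at any response, already gives 15.5% at n1 = 9. Letting N follow the data adds 16.2 − 15.5 = 0.7 points. The rest comes from the lower bar at 13 and 14, which the plan prints openly.

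**The upper figure needs a pause.** With accrual running on and 2 to 5 confirmed responses pending, the rate is about 13% to 10%. No section provides for a pause, though none forbids one, and a first PSA fall is visible before it is confirmed.

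**The purpose is administrative and there is oversight.** Closing because 3 have responded would depart from the stated purpose, and section 11.0 has the DSMC review progress and adherence. But closing at 14 breaks no written rule, so an adherence review would have nothing to find. Nothing in the documents suggests that the team intends to choose N by outcome.

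**Stage 1 might seem open to the same freedom.** It makes no material difference: the maximum is 16.53% whether n1 is 11 from the start or is extended until a first response.

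**The robustness sentence may mean modest shifts only.** In part this is fair. With half the weight on N = 15 and the rest spread evenly, the average is 0.5 × 5.47 + 0.125 × (13.13 + 15.36 + 6.68 + 8.00) = 8.1%. But weight concentrated on 14 gives 15.4% and on 15 gives 5.5%, so the sentence does not hold in general.

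**Conclusion.** The point holds in a limited form. The 10% is a valid average provided that N is unrelated to the responses, and the plan states no such requirement. Over the permitted combinations type I error runs from 5.3% to 15.8%; at n1 = 9 it falls from 15.5% to 5.5% between N = 14 and N = 15, where the bar changes. That does not fit the unsupported statement that the errors are robust to how accrual falls out.

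Response-driven closure gives 15.2% to 16.5%, an upper bound that assumes accrual waits for results at 14. With 2 to 5 patients pending it is about 13% to 10%. The part due to N following the data is about 0.7 points above a fixed N of 14.

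All figures are exact binomial results at a true response rate of 10%; the delayed ones also rest on the closing rule assumed in step 4. The consequence is confined to whether the regimen is called worthy of further study, but one enrollment decision can reverse that conclusion.

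**What to change.** In section 12.0, and in the matching synopsis text:

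1. State that stage 1 is the first 9, and the final analysis the first 15, eligible and evaluable patients in order of enrollment.
2. Allow another N within 7–11 or 13–17 only when it results from over- or under-accrual, through a dated accrual-closure decision made and documented on logistics without reference to PSA responses.
3. Report the type I error for the realized N, or the 5.3–15.8% range over permitted combinations, beside the 10% average.
4. Remove the closing robustness sentence, or qualify it with these figures.

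Keeping PSA counts out of the monthly meeting in section 11.0 would not be a safeguard. Sections 5.10 and 8.2 have investigators act on each patient's PSA, so they know the results anyway. The protection has to come from the enrollment-order rule and the documented reason for closure.

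**Cost.** A few sentences and no added patients. The team gives up discretion over when to close within 13–17. At the target 9/15 design, power is 90.8% rather than the 93% average, and type I error is 5.5%.
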